# **Data Monitoring**

Our procedures will follow the NHLBI guidelines on DSMBs that was released October 2011 (http://www.nhlbi.nih.gov/funding/policies/dsmpolicy.htm). Specifically, in consultation with NHLBI, 4 DSMB members have been appointed. The Board includes a psychiatrist, cardiologist, psychologist and biostatistician with experience in prospective interventional trials and behavioral and/or psychosocial cardiology trials. The chair will have additional duties to review past minutes, conduct the meetings and review minutes prepared by the executive secretary. The DSMB developed an operational plan during the first six months of the study. The operational plan is similar to current plans the principal investigator has developed for ongoing trials funded by NHLBI and consistent with NHLBI's Policy on Human Subjects Research: Data and Safety Monitoring Plans dated October 2011. The plan includes conflict of interest disclosure statements for each member, frequency and location of meetings, policies and procedures and dissemination of meeting materials, notification of NHLBI staff, data to be reviewed and procedures for evaluating data and reporting findings. The specific study functions and outcomes that the DSMB will review at each meeting include: dropout rate, baseline PHQ-8 scores, CES-D10 scores, and number receiving AHA diagnosis and treatment portions of the intervention protocol. The primary safety measures will be adverse events reports and 18-month PHQ-8 scores. Other items reviewed by the DSMB at each meeting will include: (a) data quality, completeness, and timeliness; (b)recruitment performance of each site; (c) adequacy of compliance with goals for recruitment and retention, including women and minorities; (d) protocol adherence; and (e) presence of factors that could adversely affect participant safety, study outcome or compromise data confidentiality.

The Data Manager, under the direction of [name], will provide the DSMB with data reports on numbers of participants recruited into the trial, participant outcomes, and serious adverse reactions on a twice-yearly basis, or as determined by the DSMB. All investigators on this grant will be the decision-making body to implement policies and procedures and follow directives of the DSMB. The DSMB will determine if unanticipated events are related to the study, whether the study's informed consent form and process needs to be modified, whether the study's procedures need to be modified and whether the study should be discontinued due to serious adverse outcomes in either the control groups or in the intervention group. All data provided will be provided in a blinded fashion. The Steering Committee will serve as an additional oversight body to determine if the DSMB should be asked to meet sooner than anticipated based on the operational plan.

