who are randomized to the AHA Depression Screen, Notify & Treat arm will also complete a PHQ-8 assessment, and those with clinically significant scores (≥ 10) will be offered the option of receiving treatment for their depressive symptoms. Participants will be presented with the option of receiving medication therapy (sertraline or bupropion), Cognitive Behavioral Therapy (delivered via phone), a combination of both therapies or neither therapy. Depending on their treatment choice, they will be scheduled for their initial treatment visit, ideally within two weeks of randomization. Their PCP and/or cardiologists will also be notified if they have clinically significant scores (≥ 10) on the PHQ-8 assessment. Those randomized to No Depression Screen group will not receive the depression screen PHQ-8 at baseline.

All participants, regardless of randomization assignment, will complete the CES-D10, SF-12 health-related quality of life measure, symptoms checklist and lost productivity at enrollment and after 6-, 12-, and 18-months of study participation. All participants will also complete the PHQ-8 assessment at 18-months, with referral to treatment for those with scores ≥ 10. Participants will be contacted by telephone, or have an in-person visit scheduled, as they prefer. These administration methods have been compared in past studies and found to be equivalent. These follow-up contacts will be brief, and scheduled at the participant's convenience wherever possible.

All participants will report their health service utilization at 6-, 12- and 18-months. Additionally, all will have EMR searches of health care utilization extracted for the 18-month duration of the trial.

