#### **Harms**

Since CODIACS-QOL is a screening trial, and not a treatment trial, the DSMB did not outline a list of reportable adverse events. However, given the nature of our population, and that some trial arms will be receiving therapy(ies), we have listed unanticipated AEs that must be reported to the DSMB according to the following guidelines.

The risk to participants will be minimal as the subjects will receive at least their usual medical care. We know of no study that has found that the type of intervention proposed

here has been associated adverse risk. Any adverse event (AE) or unanticipated problem will be identified, responded to, recorded by the site investigator, who will in turn ensure that the information is passed on (see Table below). If the AE or problem is unexpected, related to study involvement, and puts the participant at increased risk, it will be reported to the local IRB immediately, in accordance with local policies. These events will also be reported to Columbia University, which will collect and disseminate the information to the other sites and the DSMB. All other AEs and problems will be reported at the time of the biannual DSMB meetings. As this is a screening trial with a commonly used instrument, it is expected that no such events will occur.

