7. SAFETY/ TOLERABILITY

7.1 Primary (pre-specified) Safety Outcomes

Harms attributable to use of antidepressant medications (i.e., appetite problems, sleep problems, gastrointestinal upset, and bleeding) will be assessed through patient interview. Group differences in the prevalence of these potential adverse effects will be compared using chi-squared tests.

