7.2 Mortality

Mortality will be assessed by surveying patient surrogates and through review of the electronic medical record. Group differences in mortality will be compared using chi-squared tests.

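### The protocol and SAP name different primary safety measures, and the SAP plans no between-arm comparison of the 18-month PHQ-8 or of recorded adverse events

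*Protocol*

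**What the plan says.** The Protocol names its safety measures once, under Data Monitoring: "The primary safety measures will be adverse events reports and 18-month PHQ-8 scores".

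Both are collected in every arm:

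- **PHQ-8.** Under Interventions: "All participants will also complete the PHQ-8 assessment at 18-months, with referral to treatment for those with scores ≥ 10". Table 1 in Participant Timeline agrees. Only the baseline PHQ-8 is withheld from the No Screen arm.
- **Adverse and unanticipated events.** Under Harms, the site investigator records any such event. The most serious are expedited, and for the rest: "All other AEs and problems will be reported at the time of the biannual DSMB meetings". Table 1 lists an Unanticipated Event Report among the follow-up forms, and Baseline and Follow-Up Assessments counts unanticipated events as research data. The Harms section adds that "the DSMB did not outline a list of reportable adverse events".

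The SAP's safety section has two parts. Section 7.1, "Primary (pre-specified) Safety Outcomes", reads: "Harms attributable to use of antidepressant medications (i.e., appetite problems, sleep problems, gastrointestinal upset, and bleeding) will be assessed through patient interview". It continues: "Group differences in the prevalence of these potential adverse effects will be compared using chi-squared tests". Section 7.2 covers deaths: "Group differences in mortality will be compared using chi-squared tests".

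**The concern.** The same label, primary safety, is attached to two different lists. A statistician who follows the SAP would report four solicited symptoms and mortality. The report would contain no between-arm result for either measure that the Protocol calls primary.

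This matters because the two lists address different harms. The SAP's symptoms concern the possible cost of treating, which falls mainly on the Screen, Notify & Treat arm. The PHQ-8 at the end of follow-up concerns the possible cost of not treating: whether more patients in the No Screen or Screen & Notify arms finish above the trial's own screening threshold. Investigator-recorded events would catch harms that nobody thought to ask about. A safety conclusion drawn only from SAP section 7 would be silent on the last two.

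**Working it through.** No figure is in dispute, so the check is a comparison of texts.

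| Item | Protocol | SAP |
|---|---|---|
| 18-month PHQ-8 | Primary safety measure (Data Monitoring); collected in all arms | No analysis; the PHQ-8 appears only as the post-randomization screen in two arms (section 3) |
| Investigator-recorded adverse and unanticipated events | Adverse event reports are a primary safety measure (Data Monitoring); recording and reporting set out under Harms | No summary or comparison |
| Appetite, sleep, gastrointestinal and bleeding complaints | Not named as a primary safety measure | Primary safety outcomes, chi-squared tests (7.1) |
| Mortality | Enters the QALY calculation | Safety outcome, chi-squared tests (7.2) |
| CES-D10 | Collected at all four visits; used for depression-free days | Secondary efficacy, as cumulative depression-free days (8) |

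1. **Overlap of the two primary lists.** Of the Protocol's two measures, the SAP's safety outcomes include none. Of the SAP's four, the Protocol names none as a primary safety measure.
2. **Whether another section fills the gap.** The Protocol's Statistical Methods contain no safety analysis. SAP 5.2 plans interim looks for safety but names no measure. SAP 8 analyses only the CES-D10 for depression, accumulated over 18 months.
3. **Whether the difference is explained.** The Protocol's summary of changes has no entry on safety measures, and the SAP gives no reason for its choice.
4. **Whether the comparison is feasible.** The blinded coordinator runs the 6-, 12- and 18-month assessments on one schedule for all arms. A by-arm PHQ-8 table at 18 months therefore needs no new data.

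**The case against.** The strongest reply is about context. The Protocol sentence sits between two others that list what the DSMB reviews at each meeting, and the one that follows speaks of other items the board reviews. On that reading it describes what the board watches, and the SAP is free to define final-analysis outcomes separately. This reading is tenable. It is not the only one, because the sentence itself carries no such limit. It also leaves the gap in place: the Protocol says that the board's data are supplied blinded, and neither document says how the 18-month PHQ-8 would be compared between arms. A score taken at a participant's last visit is also a late signal for monitoring and a natural quantity for a final comparison.

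Three stronger inferences that a reader might draw are not supported:

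- **That the PHQ-8 is the only check on depression at the end of the trial.** The CES-D10 is also given to everyone at 18 months, and the SAP analyses it across the three arms. What is missing is a comparison of status at 18 months, since depression-free days are cumulative.
- **That the 18-month PHQ-8 scores would go unused.** They go to the DSMB and trigger referral or provider notification at 10 or above (Interventions; Post-trial care). They lack only a planned comparison.
- **That side effects are the SAP's whole safety analysis.** Mortality is compared too, and the four symptoms are themselves possible adverse effects. They are solicited at interview, however, and are not the investigator-recorded events described under Harms.

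Two cautions about the added tables also stand. With no fixed list of reportable events, and closer contact with participants in study treatment, event counts may differ between arms through ascertainment alone. And the PHQ-8 is self-reported by unblinded participants. SAP 5.3 itself gives reporting bias as a reason to prefer QALYs to a direct measure of depression. Both are reasons to interpret the tables carefully, not to leave them out.

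**Conclusion.** The point holds in a limited form. The two documents attach the primary safety label to lists that do not overlap, and the SAP plans no between-arm analysis of the 18-month PHQ-8 or of recorded adverse and unanticipated events. Whether the Protocol promised a final comparison depends on whether its sentence extends beyond DSMB monitoring, and the text does not settle that. The documents must therefore be reconciled, but they do not show that a committed analysis was dropped.

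The size is best stated as coverage: neither of the Protocol's two named measures is among the SAP's safety outcomes. The defect is one of specification, so no power or error-rate figure measures it. It bears on the safety conclusion only. The primary QALY analysis, its test procedure and its sample size are untouched.

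**What to change.** In SAP section 7, keep the side effects and mortality, and add:

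- **18-month PHQ-8 by arm:** mean and proportion scoring 10 or above, with the three pairwise differences and 95% confidence intervals for each summary. Show the number assessed per arm, and state how deaths and missing scores are handled, since SAP 5.6 does not mention the PHQ-8.
- **Adverse and unanticipated events by arm:** counts of events and of participants with at least one, presented descriptively with a note on ascertainment.

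Then use one definition of the primary safety measures in both documents. If the Protocol sentence was meant for DSMB monitoring only, say so there and in SAP 7.1. While that text is open, state the time point for the symptoms in 7.1 and reword SAP 4.2, which rules out analyses on a safety sample although 4.3 goes on to define one.

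The cost is two tables, some wording, and a few more unadjusted comparisons: two PHQ-8 summaries times three pairs of arms gives 2 × 3 = 6 intervals. They should be labelled as safety estimates outside the familywise error control of the QALY test. No new data collection is needed.

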#### **Harms**

Since CODIACS-QOL is a screening trial, and not a treatment trial, the DSMB did not outline a list of reportable adverse events. However, given the nature of our population, and that some trial arms will be receiving therapy(ies), we have listed unanticipated AEs that must be reported to the DSMB according to the following guidelines.

The risk to participants will be minimal as the subjects will receive at least their usual medical care. We know of no study that has found that the type of intervention proposed

here has been associated adverse risk. Any adverse event (AE) or unanticipated problem will be identified, responded to, recorded by the site investigator, who will in turn ensure that the information is passed on (see Table below). If the AE or problem is unexpected, related to study involvement, and puts the participant at increased risk, it will be reported to the local IRB immediately, in accordance with local policies. These events will also be reported to Columbia University, which will collect and disseminate the information to the other sites and the DSMB. All other AEs and problems will be reported at the time of the biannual DSMB meetings. As this is a screening trial with a commonly used instrument, it is expected that no such events will occur.

# Adverse Events and Unanticipated Problems Reporting Timelines (modified from NHLBI guidelines on reporting SAEs and Ups)

What Event is Reported	When is Event Reported	By Whom is Event Reported	To Whom is Event Reported
Fatal or life- threatening unexpected, suspected serious adverse reactions	Within 7 calendar days of initial receipt of information	Investigator	Local/internal IRBs/Institutional Officials Study coordinating center (who in turn report to DSMB)
Non-fatal, non-life- threatening unexpected, suspected serious adverse reactions	Within 15 calendar days of initial receipt of information	Investigator	Local/internal IRBs/Institutional Officials Study coordinating center (who in turn report to DSMB)
Unanticipated Problem that is not an SAE	Within 14 days of the investigator becoming aware of the problem	Investigator	Local/internal IRBs/Institutional Officials Study coordinating center (who in turn report to DSMB

Should a study-participation related, unexpected adverse event occur, the study cardiologist ([name]) and/or study psychiatrist ([name]) will review the circumstances of the event and report accordingly to the DSMB. Any serious adverse effects will be reported to the CUIMC IRB. If any adverse outcomes might influence the continued participation of the participants, active participants will be informed. All participants will be provided contact information instructed to contact either the study coordinator or local PI in the event the participant would like to discuss any study-related issue or adverse event that arises.

# **Procedures for Side Effects Due to Study Antidepressants:**

Participants will have all possible side-effects carefully described and explained before any course of anti-depressants is initiated. Site medication providers have undergone thorough training on the detection and management of side-effects with [name], who remains available for consultation with the site medication prescribers. Below is an overview of what was taught, and will be followed for the trial:

# Strategies for Managing Antidepressant Side Effects General Strategies:

- 1. Explore whether the side effects are 'physical' or 'psychological'?
- 2. Wait and support. Many side effects (i.e., GI depressive symptoms with SSRIs) will subside over 1-2 weeks of treatment.
- 3. Lower the dose (temporarily).
- 4. 'Treat' the side effects (see below).
- 5. Change to a different antidepressant.
- 6. Change to or add psychotherapy.

#### **Antidepressant Drug Interactions:**

All antidepressants are metabolized by the P450 isoenzyme system in the liver. Certain antidepressants inhibit specific subtypes of P450 enzymes and this may increase blood levels in participants who are taking other medications metabolized by the same isoenzyme systems. Care is advised in participants who are taking medications with a narrow therapeutic window such as digoxin, warfarin, anticonvulsants, or theophylline. It is advised to **observe clinically for side effects** from such medications and **to recheck serum blood levels** of such medications as the dose of the antidepressant is titrated upwards.

# **Procedures for Discontinuation Syndrome:**

Abrupt discontinuation of short acting antidepressants can lead to an uncomfortable antidepressant withdrawal syndrome. All participants choosing anti-depressants will have this carefully explained, and will be monitored (by self-report) for continued adherence to their prescribed anti-depressant. Any participant reporting symptoms consistent with withdrawal syndrome will be reminded that their symptoms could be due to cessation of anti-depressant adherence, and will be urged to taper, rather than cease their medication use. Tapering will also be considered as appropriate when at stepped care decision points, an alternative medication is recommended

Any AE or unanticipated problem will be identified, responded to, recorded by the site investigator, who will in turn ensure that the information is passed on. If the AE or problem is unexpected, related to study involvement, and puts the participant at increased risk, it will be reported to the local IRB immediately, in accordance with local policies. These events will also be reported to Columbia University, which will collect and disseminate the information to the other sites and the DSMB. All other AEs and problems will be reported at the time of the biannual DSMB meetings.

#### Auditing

Routine audits of data completion and timeliness will be overseen by the study data manager.

# **Ethics and Dissemination**

# **Research Ethics Approval**

This protocol and the template informed consent forms have been approved by Columbia University's Institutional Review Board (IRB) with respect to scientific content and compliance with applicable research and human subjects regulations. The, participant education and recruitment materials, data collection forms, and Intervention manual have also been approved by the CUIMC IRB. Any subsequent modifications will also be reviewed and approved by the CUIMC IRB. Respective local site IRBs are required to approve protocol materials and a site-specific informed consent form. Each study site must submit verification of IRB approval to the Coordinating Center prior to the initiation of study activities.

Subsequent to initial review and approval, Columbia University's IRB, and the responsible local IRBs will review the protocol at least annually. The overall PI and site PIs will make safety and progress reports to the IRBs at least annually and within three months of completion of study visits. or completion at his/her site. These reports will include the total number of participants enrolled, reports to the DSMB, and any other requested reports.

#### **Protocol Amendments**

Any modifications to the protocol which may impact on the conduct of the study, potential benefit of the patient or may affect patient safety, including changes of study objectives, study design, patient population, sample sizes, study procedures, or significant administrative aspects will require a formal amendment to the protocol. Such amendment will be agreed upon by the overall PI, site PIs and co-investigators, and approved by the DSMB and responsible IRB prior to implementation and notified to the health authorities in accordance with local regulations.

Administrative changes of the protocol are minor corrections and/or clarifications that have no effect on the way the study is to be conducted. These administrative changes will be agreed upon by the overall PI and site PIs, and will be documented in a memorandum. The responsible IRBs may be notified of administrative changes at the discretion of the PIs.

#### **Informed Consent**

The protocol and informed consent procedures will be approved by the Institutional Review Boards at each participating institution. Consent forms will be worded in language that a person with a 6th grade education can understand and will be available in English. At the time of enrollment, the staff member will give a complete description of the study to the participant in clear, easy-to-understand language. After reading and understanding the consent and the procedures, those who choose to participate will sign and date the consent.

All staff involved in this study will have completed and passed GCP and HIPAA training, and will have been provided with materials and instruction in the proper and ethical

manner in which consent should be obtained. If a web-based or telephone consent is obtained, it will comply with all GCP and HIPAA regulations, and be IRB-approved.

# Confidentiality

As part of the process involved in obtaining written informed consent, all participants will be reminded that their responses are confidential and that they may refuse to participate in the study or withdraw at any time without explanation, and further, that such an action will in no way affect their future interactions with their health care provider or the participating Medical Center.

To ensure confidentiality, all study-related information will be stored securely at the study sites. When paper records are obtained, those containing names or other personal identifiers, such as locator forms, medical records, and informed consent forms, will be stored separately from study records identified by participant ID number. Forms, lists, logbooks, appointment books, and any other listings that link participant ID numbers to other identifying information will be stored in a separate, locked file in an area with limited access. All databases will be secured with password-protected access systems. Datasets for analysis will be associated with an individual participant only by an assigned identification number.

All staff will have all relevant IRB and HIPAA training in the protection of human subject participants (Good Clinical Practice).

